	Group A (Intervention Group Group A will receive the developed intervention tool comprising a Brief Intervention (FRAME Model). An online meeting will be arranged with a trained, peer counsellor to discuss drug use behaviour and to provide support and motivation to change. After the brief counseling, participant will then be directed to the Chemsex Care Plan, a self-directed interactive program that participants can access anytime at their convenience and will provide participants access to online materials (videos, infographics, etc) to educate stimulant-using MSM on reducing risky drug-use behaviour, as well as goal-setting. Participant will be asked to complete a brief survey at 6-week and 12-week follow-up to assess the drug use behavior and motivation to change.
	Group B (Control Group) Group B will receive a self-help toolkit from the World Health Organization for cutting down and stopping drug use. Participant is encouraged to use the toolkit to manage their drug use for 12 weeks. Similar to Group A, they will then be asked to complete a follow-up survey after 6 weeks and 12 weeks. After the end of the study, they will be given access to the Chemsex Care Plan.

	Randomization							
	Participants who agree to the follow-up study are sent a link and a							
	password (unique password for each participant) to log onto the study							
	website. Those logging on are randomized in 1:1 ratio with no							
	stratification to receive their respective materials.							
Study outcomes	The development of the online intervention addresses the worsening HIV							
	epidemic in a subpopulation of MSM in Malaysia. This pilot study							
	collects the feasibility, acceptability, and preliminary efficacy of ASSIT-							
	Brief Intervention and Chemsex Care Plan to reduce harms related to							
	drug use and sexual risk among MSM.							
Measurements	Primary outcome measure							
	Stimulant use severity is measured using e-ASSIST (eASSIST; measured							
	at baseline and 12-week follow-up)							
	- /							
	Secondary outcome measures							
	Measured at baseline, 6-week, and 12-week follow-up:							
	1. Number of days stimulants used in the last 30 days							
	2. Depression, Anxiety, and Stress Scale - 21 Items (DASS-21)							

Project Summary

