2.4. Data analysis

2.4.1. Outcome variables

The primary outcome variable is the eASSIST (eASSIST; measured at baseline and 12-week follow-up) which indicates stimulant use severity (Gryczynski et al., 2015). The secondary outcome variables, number of days stimulants used in the last 30 days and the Depression, Anxiety and Stress Scale - 21 Items (DASS-21) will be measured at baseline, 6-week and 12-week follow-up. Among HIV-negative participants, willingness to access PrEP and utilization of PrEP will be assessed while among HIV-positive participants, linkage to HIV services and adherence to ART will be assessed at the 12-week follow up. Additionally, data on utilization of HIV/STI services at the community-friendly clinics will be extracted from the HIV/STI monitoring database by Malaysian AIDS Council using the unique client ID.

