2.4.2. Analysis plan

Bivariate comparisons of baseline demographic and outcome variables will be conducted. Outcome analyses will employ mixed effect repeated measures outcomes and used all available data for each time point. Overall, 3 separate mixed-effect models will be conducted to examine the effect of time, intervention condition, and the time by intervention condition on each outcome variable. Missing data will be analysed using a maximum likelihood approach.

[figure not shown]

Figure 2. Study Flowchart

3. Online Intervention

The online intervention will comprise two components: 1) **Brief Intervention (FRAME model)** to be administered by case workers online, and 2) **Chemsex care Plan**, a self-directed, interactive online material that participants can access anytime, at their convenience.

[figure not shown]

Figure 3. Online intervention flow chart

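### The primary eASSIST model cannot use the week-6 data of men lost later, which leaves the 12-week comparison open to drop-out bias that those data could reduce

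*Protocol*

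**What the plan says.** Section 2.4.1 reads "The primary outcome variable is the eASSIST (eASSIST; measured at baseline and 12-week follow-up"). The synopsis gives the same two occasions, under "Stimulant use severity is measured using e-ASSIST (eASSIST; measured". The secondary outcomes, "number of days stimulants used in the last 30 days" and DASS-21, "will be measured at baseline, 6-week and 12-week follow-up".

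Section 2.4.2 sets the analysis: "Overall, 3 separate mixed-effect models will be conducted to examine the effect of time, intervention condition, and the time by intervention condition" for each outcome. The models "used all available data for each time point", and "Missing data will be analysed using a maximum likelihood approach". No joint model, auxiliary variable or imputation step is named.

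Two places pull the other way on timing. Section 5 (Evaluation by participants) says the 6-week survey repeats questions matched to baseline and points to section 2.2, which includes eASSIST. The sample size section speaks of an intervention effect at both follow-ups. The synopsis and section 2.4.1 are the more explicit statements and are followed here.

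**The concern.** With one post-baseline value per man, maximum likelihood can condition drop-out only on arm and baseline eASSIST. It is valid for the primary outcome only if, given those two, loss is unrelated to how the man used drugs after randomisation. The trial measures that use at week 6, but the primary model as specified does not see it.

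The unused measure is closely related to the outcome. Week 6 is day 42, so its 30-day window runs from day 12 to day 42. Week 12 is day 84, and the ASSIST recall period of three months (about 90 days) reaches back to about day −6. The week-6 report therefore covers part of the period that the missing week-12 score would have described.

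Loss could plausibly be linked to use, and differently by arm. Group A has a live session with a counsellor, and case workers can help with clinic visits. Group B has a self-help toolkit, with the Chemsex Care Plan offered after three months. If heavier users in Group A leave more readily, Group A looks better at week 12 than it is.

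**Working it through.** **The plan's own figures.** The protocol gives no figure for missing-data bias. Its sample size is reproduced: the noncentrality is 0.53 × √(94/2) = 3.6335, the critical t on 186 df is 1.9728 and power is 0.951, as stated. The target of 226 is 188 × 1.2 = 225.6, or 113 per arm. At 20% attrition, 0.20 × 226 ≈ 45 men lack a week-12 score. Only those lost after week 6 have week-6 data to recover.

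**Assumptions (none is in the documents).** X is baseline eASSIST, U is week-6 use and Y is week-12 eASSIST, all normal with SD 1.
- ρ(X,U) = 0.5; ρ(X,Y) = 0.5 to 0.65; ρ(U,Y) = 0.5 to 0.65.
- No true effect; 20% lost per arm unless stated.
- Either all loss follows week 6, or half does and the earlier half is random.
- Loss after week 6 is logistic in U.

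**Bias formula.** Let m be the mean of U among completers in an arm. Completers then have mean Y of ρ(U,Y)·m and mean X of ρ(X,U)·m. The two-occasion model corrects for X with slope of about ρ(X,Y), which leaves

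bias in one arm ≈ [ρ(U,Y) − ρ(X,U)·ρ(X,Y)] × m.

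The bias in the comparison is the Group A value minus the Group B value; negative favours Group A.

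**Values of m.** m = E[U·(1 − p(U))] / (1 − loss rate), by numerical integration with the intercept set to give the loss rate.
- Log-odds +1 per SD (odds ratio 2.7), 20% lost: −0.173. At 15% lost: −0.133. At 25% lost: −0.213.
- Log-odds +0.3, 20% lost: −0.059.
- Odds ratio 0.6, 20% lost: +0.098.

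**Bias when all loss follows week 6, ρ(X,Y) = 0.5, ρ(U,Y) = 0.65.** The bracket is 0.65 − 0.25 = 0.40.
- Dependence in Group A only: 0.40 × (−0.173) = −0.069.
- Opposite directions (2.7 in A, 0.6 in B): 0.40 × (−0.173 − 0.098) = −0.108.
- Weaker in Group B (log-odds 1 against 0.3): 0.40 × (−0.173 + 0.059) = −0.046.
- Same slope, 15% lost in A and 25% in B: 0.40 × (−0.133 + 0.213) = +0.032.
- Same slope, same rate: 0.

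**False-positive rate.** The variance of the two-occasion change estimate per arm is (1 − 0.5²)/90.4 + (1 − 0.5)²/113 = 0.00830 + 0.00221 = 0.01051. The SE of the arm difference is √(2 × 0.01051) = 0.145. A bias of 0.071 is 0.49 SE, giving a two-sided rejection rate of 7.8%. A bias of 0.110 is 0.76 SE, giving 11.8%.

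**Simulation with the same correlations** (these biases allow for small departures from the linear formula):

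| Loss depends on week-6 use | All loss after week 6: bias (rejection) | Half after week 6: bias (rejection) |
|---|---|---|
| Group A only | −0.071 SD (7.7%) | −0.041 SD (5.9%) |
| Opposite directions | −0.110 (11.7%) | −0.063 (7.1%) |
| Weaker in Group B | −0.047 (6.2%) | −0.028 (5.4%) |
| Same slope, loss 15% v 25% | +0.035 (5.6%) | +0.021 (5.2%) |
| Same slope, same rate | 0.00 | 0.00 |

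With week-6 use in the analysis, the bias is within 0.001 SD, rejection is 5% and the SE falls by 1 to 2.5%.

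**Sensitivity to the correlations.** With ρ(X,Y) = 0.65 and ρ(U,Y) = 0.5, the bracket is 0.5 − 0.325 = 0.175. Group A only then gives 0.175 × (−0.173) = −0.030, and opposite directions gives 0.175 × (−0.271) = −0.047. In the other direction, mirror-image dependence (log-odds +1 and −1) with ρ(X,Y) = 0.5 and ρ(U,Y) = 0.7 gives 0.45 × (−0.346) = −0.16. That takes a more extreme mechanism than the cases tabulated.

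**The case against.** The strongest reply is that a mixed model with maximum likelihood is standard, and that auxiliary variables and imputation models usually belong in the SAP, which is not shown. Much of this stands: an SAP could add them, and the protocol does not forbid it. But the protocol does not leave the matter open. It names the missing-data method and one model per outcome, and as written these leave the week-6 measures out of the primary result.

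The arm-specific premise is also thin. The counselling is a single session of about 20 minutes, followed by a self-directed programme. The survey schedule, vouchers and WhatsApp reminders are described without any difference by arm. A higher baseline to week-12 correlation than 0.5 is credible too, because ASSIST items 6 and 7 still score 3 for events more than three months ago. Both points limit the size of the problem; neither removes it.

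Three stronger readings are tempting, and the documents do not support them:
- A reader might infer that the primary result is biased. Nothing shows the required drop-out pattern, and the bias is zero when dependence and loss rates are equal across arms.
- A reader might infer that the week-6 data are thrown away. They enter the models for stimulant-use days and DASS-21.
- A reader might infer that the plan breaks its own promise, since its models "used all available data for each time point". The fair reading is that men with incomplete follow-up stay in each outcome's model, not that information is pooled across outcomes.

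**Conclusion.** The point stands as a conditional weakness. As specified, the primary comparison relies on a stricter drop-out assumption than the collected data require. Under the assumptions listed, with 20% loss and half to all of it after week 6, the removable bias is 0 to about 0.1 SD, typically 0.02 to 0.07 SD. The false-positive rate is 5% to about 12%, and the upper end needs opposite-direction dependence with every loss after week 6. Against the design effect of 0.53 SD this is modest.

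The correlations and the drop-out mechanism are assumed throughout. If eASSIST is in fact asked at week 6, as section 5 suggests, the weakness is the same but the remedy is simpler. Priority: low to moderate, as a cheap improvement.

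**What to change.** In section 2.4.2, state that the primary 12-week eASSIST comparison will use stimulant-use days and DASS-21 at week 6 as auxiliary information. This can be done through a joint likelihood model of eASSIST and stimulant-use days, or through multiple imputation by arm. Keep the two-occasion maximum-likelihood model as a sensitivity analysis.

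Reconcile section 5 with the synopsis and section 2.4.1 on whether eASSIST is asked at week 6. If it is, include that score in the primary repeated-measures model.

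The cost is a sentence or two and some programming, with no new data and no more men. The imputation model must suit a skewed 0 to 30 day count, for example by predictive mean matching. The change does nothing for men lost before week 6, and it does not correct for loss driven by use after week 6.

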3.1 Brief Intervention (FRAMES model)

Participants will be asked to schedule an appointment to interact virtually with the case workers from the NGO to receive brief intervention after completing eASSIST. A personal chatroom will be opened for the case worker and participants to enhance anonymity and privacy. Participants may request video conference when they feel comfortable to do so. Following the screening questions from e-ASSIST, the case workers or peer counsellor will provide brief intervention (BI) which included the discussion of the scores of the eASSIST Feedback Report card and use of motivational Interviewing (MI) techniques to assess and motivate clients to change drug use behaviors. The principles underlying most approaches to BI were systemized by Miller and Sanchez (1994) in a FRAMES model which comprised of:

- Feedback: Give feedback on the risks and negative consequences of substance use.
- **Responsibility**: Emphasize that the individual is responsible for making his or her own decision about his/her drug use.
- Advice: Give straightforward advice on modifying drug use.
- **Menu of options**: Give menus of options to choose from, fostering the client's involvement in decision-making.
- Empathy: Be empathic, respectful, and non-judgmental.
- **Self-efficacy**: Express optimism that the individual can modify his or her substance use if they choose. Self-efficacy is one's ability to produce a desired result or effect.

The eASSIST-linked BI aimed at reducing illicit substance use and related risks is shown to be effective in different countries (Humeniuk et al., 2012). The brief intervention is based on the approach of motivational interviewing, which is a directive, client-centered counselling method developed from experience of alcoholism treatment by Miller. Several randomized clinical trials showed that MI is effective for reducing alcohol and substance use in general populations as well as in MSM (Morgenstern J 2009, William Zule 2012, Parson et al. 2014, Parson et al. 2018). Furthermore, MI is listed as one of the best behavioural interventions for HIV risk reduction by the US Centers for Disease Control and Prevention, http://www.cdc.gov/hiv/topics/research/prs/best-evidence-intervention,htm).

The brief intervention takes approximately 20 minutes to complete. During BI, the peer counsellor/case worker will elicit the participants' view of drug use behaviour, focused on increasing the commitment and confidence to change, and developing a personalized plan to maintain the change.

10 STEPS OF

BRIEF INTERVENTION

[figure not shown]

Figure 4. Brief Intervention

There are unique challenges for MSM in reducing or stopping stimulant drug use which need to be addressed during the brief intervention. The adaptation of ASSIST-brief intervention will aim to address the dual, parallel risky behaviors: stimulant drug use and risky sexual behaviors. Therefore, participants will be given a brief counselling on HIV and STI testing, highlighting the importance of knowing one's HIV/STI status and immediate treatment upon diagnosis. Other biomedical prevention methods such as PrEP and PEP will be prioritized as consistent condom use may be unrealistic during chemsex. Specifically, on-demand PrEP will be beneficial for those who engage in chemsex party during weekend or public holidays. Contact information of MSM-friendly HIV and STI clinics will be provided on the website. Case workers will assist with making appointment with the clinics and offer support to accompany participants to access HIV/STI services. For participants who are diagnosed with HIV prior to the study, engagement in care and concept of "Undetectable=Untransmissible" will be emphasized during the brief counseling.

3.2 The Chemsex Care Plan

Chemsex Care Plan is developed by chemsex counselor from the renowned sexual health clinic (56 Deans' Street). The Chemsex Care Plan is based on motivational interviewing and has incorporated elements of cognitive behavioral therapy. To adapt the chemsex care plan to suit the Malaysian context, attractive online materials will be developed in order to reach MSM who use stimulant drugs. These materials will include short videos, infographs, animations, etc. The following is the flow of the Chemsex Care Plan:

- a) Setting life goals. Recognizing the participants may be at different level of readiness to reduce or quit using stimulant drugs, the care plan first asks clients to select their current goal related to drug use: 1) Abstinence, 2) Take a short break, 3) Play more safely, and 4) Still not sure what I want to do. Depending on the stages of change participants will be directed to subpage that would best match their need. Additionally, it asks participants their confidence in meeting those goals and the importance of making these goals.
- b) For those who select "abstinence" as their goal, they will be directed to a webpage with several education videos that to affirm their motivation and to In these videos, participants will be asked to reflect on their sex lives, the time when they had sober sex and social activities they might have missed during their active use of stimulant drugs. Participants will learn to change their social and physical environment to support their recovery.
- c) For those who prefer to "taking a short break," they will be asked to set plan and goal for abstinence for a short period of time. They will be given suggestions to develop strategies to cope with cravings and maintain abstinence for a short period of time.
- d) For MSM who have no desire to quit using but who wish to "play it safely", harm reduction information will be made available to them.

4. Ethical considerations

As part of the study, a list of FAQ will serve as an avenue for participants who wish to have quick answers to their questions. A pre-set of questions and answers regarding the benefits and harms of stimulant drug use, harm reduction, existing support services will be compiled and laid out in a simple format. A hotline number will be available on the website for research team to answer questions related to the study at designated time during weekdays. Participants will be reminded by WhatsApp message to conduct the follow-up surveys. All intervention materials will be delivered online; there will be no physical interaction between participants and research team members. No personal identifying information such as names or identification number will be collected from the participants. Instead, unique ID number will be used to identify the participants. Reminder message sent to participants will not reveal participant's status of participating in a study pertaining drug use and HIV.

Online Informed consent will be obtained before participants are enrolled to the study. Participants will be informed of the study design, study procedure and duration, potential risk and benefits of the study. Furthermore, participants will be asked not to reveal any identifying information such as their name and location during the brief intervention. Permission to audio record the brief intervention will be obtained from the participant before beginning of the intervention. The main purpose of the audio recording to verify and evaluate the counseling session and ensure that caseworkers' administration of the Brief Intervention according to the study protocol; all identifying information will be removed prior to review and recordings will be deleted after verification data has been obtained.

5. Adaptation Process

Experts in intervention development and delivering HIV prevention and substance abuse treatment services to stimulant using MSM will be formally engaged. The research team will include a psychiatrist, a public health researcher, a master's-level project director, and two external experts from University of Adelaide and National Cheung Kung University. The research team will conduct bi-monthly meetings with the local community members and services providers to modify the intervention for application in a community setting.

Training of case workers. Case workers from the CBO will undergo formal training in the following:

- 1) Stimulant drug use, ASSIST/brief intervention (1 Day) by [name] from Hospital Kuala Lumpur and [name] from University Malaya Centre of Addiction Science (UMCAS), University Malaya. The workshop will cover the overview of stimulant drug use and psychosocial interventions for stimulant use disorder. Existing mental health and support services for drug abuse will also be discussed.
- 2) ASSIST-brief intervention (3 Days) by [name] from University of Adelaide (online training). Basic skills on drug counseling and delivering education materials will be imparted to case workers. After the training, peer counsellors will role play in administering ASSIST-brief intervention. The training will be evaluated by the [name] and the research team. A certificate will be given case workers who are qualified to administer ASSIST-brief intervention.
- 3) Chemsex Care Plan, interviewing skills and issues pertaining to chemsex and drug use recovery from [name] (online training).
- 4) HIV Pre-Exposure Prophylaxis implementation in Malaysia by [name] from University of Malaya Medical Centre (online training).

Evaluation by participants. Two types of evaluation will be asked from the participants:

- Outcomes evaluation by pre- and post-test. Participants will be asked to complete a 6-week and 12-week follow-up survey with matched questions from baseline (see section 2.2).
- **Process evaluation.** We will collect data on participation, resource use, and satisfaction of peer counselling from research staff, case workers and participants. The number of views of online intervention materials, number of clicks on the website, duration of peer counselling, and usage of Chemsex Care Plan will be recorded to monitor the activities on the online intervention.
- **Expected outcomes**: Reduction in stimulant use, reduction in risky sexual behaviors, and improvement in mental health outcomes.

Hypothesis: We hypothesize that intervention participants will demonstrate significant decrease in HIV/STI risk and methamphetamine use from baseline to follow-up surveys. Additionally, we postulate that participation in the intervention will lead to improvement in secondary outcomes, including mental health (depression), social functioning and quality of life.

Appendices

Appendix A. ASSIST (Alcohol, Smoking and Substance Involvement Screening Test)

1. In your life, which of the following substances have you ever used? (NON-MEDICAL U MEDICAL USE ONLY) 2. In the past three months, how often have you used the substances you mentioned (FIRST DRUG, SECOND DRUG, ETC)? DRUG, ETC)? Monthly=3 Weekly=4 Daily/Almost daily=6 3. During the past three months, how often have you had a strong desire or urge to use (FIRST DRUG, SECOND DRUG, ETC)? Monthly=4 Weekly=5 Daily/Almost daily=6 4. During the past three months, how often has your use of (FIRST DRUG, SECOND DRUG, ETC) led to health, social, legal or financial problems? Monthly=5 Weekly=6 Daily/Almost daily=7 5. During the past three months, how often have you failed to do what was normally expected of you because of you because of your use of (FIRST DRUG, SECOND DRUG, ETC)? Weekly=7 Daily/Almost daily=8 6. Has a friend or relative or anyone else expressed concern about your use of (FIRST DRUG, SECOND DRUG, Yes, in the past 3
(NON-MEDICAL U MEDICAL U MEDICAL USE ONLY) 2. In the past three months, how often have you used the substances you mentioned (FIRST DRUG, SECOND Once/Twice=2 Monthly=3 Weekly=4 Daily/Almost daily=6 3. During the past three months, how often have you had a strong desire or urge to use (FIRST DRUG, SECOND Once/Twice=3 DRUG, ETC)? Monthly=4 Weekly=5 Daily/Almost daily=6 4. During the past three months, how often has your use of (FIRST DRUG, SECOND DRUG, ETC) led to health, once/Twice=4 social, legal or financial problems? Monthly=5 Weekly=6 Daily/Almost daily=7 5. During the past three months, how often have you failed to do what was normally expected of you because of you once/Twice=5 because of your use of (FIRST DRUG, SECOND DRUG, Monthly=6 ETC)? Weekly=7 Daily/Almost daily=8 6. Has a friend or relative or anyone else expressed concern No, never=0
2. In the past three months, how often have you used the substances you mentioned (FIRST DRUG, SECOND Once/Twice=2 DRUG, ETC)? Monthly=3 Weekly=4 Daily/Almost daily=6 3. During the past three months, how often have you had a strong desire or urge to use (FIRST DRUG, SECOND Once/Twice=3 DRUG, ETC)? Monthly=4 Weekly=5 Daily/Almost daily=6 4. During the past three months, how often has your use of (FIRST DRUG, SECOND DRUG, ETC) led to health, social, legal or financial problems? Monthly=5 Weekly=6 Daily/Almost daily=7 5. During the past three months, how often have you failed to do what was normally expected of you because of you because of your use of (FIRST DRUG, SECOND DRUG, ETC)? Weekly=7 Daily/Almost daily=8 6. Has a friend or relative or anyone else expressed concern No, never=0
2. In the past three months, how often have you used the substances you mentioned (FIRST DRUG, SECOND DRUG, ETC)? DRUG, ETC)? Monthly=3 Weekly=4 Daily/Almost daily=6 3. During the past three months, how often have you had a strong desire or urge to use (FIRST DRUG, SECOND DRUG, ETC)? Monthly=4 Weekly=5 Daily/Almost daily=6 4. During the past three months, how often has your use of (FIRST DRUG, SECOND DRUG, ETC) led to health, social, legal or financial problems? Monthly=5 Weekly=6 Daily/Almost daily=7 5. During the past three months, how often have you failed to do what was normally expected of you because of you once/Twice=5 because of your use of (FIRST DRUG, SECOND DRUG, ETC)? Weekly=7 Daily/Almost daily=8 6. Has a friend or relative or anyone else expressed concern No, never=0
substances you mentioned (FIRST DRUG, SECOND Once/Twice=2 DRUG, ETC)? Monthly=3 Weekly=4 Daily/Almost daily=6 3. During the past three months, how often have you had a strong desire or urge to use (FIRST DRUG, SECOND Once/Twice=3 DRUG, ETC)? Monthly=4 Weekly=5 Daily/Almost daily=6 4. During the past three months, how often has your use of (FIRST DRUG, SECOND DRUG, ETC) led to health, social, legal or financial problems? Monthly=5 Weekly=6 Daily/Almost daily=7 5. During the past three months, how often have you failed to do what was normally expected of you because of you Once/Twice=5 because of your use of (FIRST DRUG, SECOND DRUG, ETC)? Weekly=7 Daily/Almost daily=8 6. Has a friend or relative or anyone else expressed concern No, never=0
DRUG, ETC)? Monthly=3 Weekly=4 Daily/Almost daily=6 3. During the past three months, how often have you had a strong desire or urge to use (FIRST DRUG, SECOND Once/Twice=3 DRUG, ETC)? Monthly=4 Weekly=5 Daily/Almost daily=6 4. During the past three months, how often has your use of (FIRST DRUG, SECOND DRUG, ETC) led to health, once/Twice=4 social, legal or financial problems? Monthly=5 Weekly=6 Daily/Almost daily=7 5. During the past three months, how often have you failed to do what was normally expected of you because of you once/Twice=5 because of your use of (FIRST DRUG, SECOND DRUG, ETC)? Weekly=7 Daily/Almost daily=8 6. Has a friend or relative or anyone else expressed concern No, never=0
Weekly=4 Daily/Almost daily=6 3. During the past three months, how often have you had a strong desire or urge to use (FIRST DRUG, SECOND Once/Twice=3 DRUG, ETC)? Monthly=4 Weekly=5 Daily/Almost daily=6 4. During the past three months, how often has your use of (FIRST DRUG, SECOND DRUG, ETC) led to health, social, legal or financial problems? Monthly=5 Weekly=6 Daily/Almost daily=7 5. During the past three months, how often have you failed to do what was normally expected of you because of you once/Twice=5 because of your use of (FIRST DRUG, SECOND DRUG, Monthly=6 ETC)? Weekly=7 Daily/Almost daily=8 6. Has a friend or relative or anyone else expressed concern No, never=0
Daily/Almost daily=6 3. During the past three months, how often have you had a strong desire or urge to use (FIRST DRUG, SECOND Once/Twice=3 DRUG, ETC)? Monthly=4 Weekly=5 Daily/Almost daily=6 4. During the past three months, how often has your use of (FIRST DRUG, SECOND DRUG, ETC) led to health, social, legal or financial problems? Monthly=5 Weekly=6 Daily/Almost daily=7 5. During the past three months, how often have you failed to do what was normally expected of you because of you Once/Twice=5 because of your use of (FIRST DRUG, SECOND DRUG, Monthly=6 ETC)? Weekly=7 Daily/Almost daily=8 6. Has a friend or relative or anyone else expressed concern No, never=0
 3. During the past three months, how often have you had a strong desire or urge to use (FIRST DRUG, SECOND Once/Twice=3 DRUG, ETC)? Monthly=4 Weekly=5 Daily/Almost daily=6 4. During the past three months, how often has your use of (FIRST DRUG, SECOND DRUG, ETC) led to health, once/Twice=4 social, legal or financial problems? Monthly=5 Weekly=6 Daily/Almost daily=7 5. During the past three months, how often have you failed to do what was normally expected of you because of you once/Twice=5 because of your use of (FIRST DRUG, SECOND DRUG, Monthly=6 ETC)? Weekly=7 Daily/Almost daily=8 6. Has a friend or relative or anyone else expressed concern No, never=0
strong desire or urge to use (FIRST DRUG, SECOND Once/Twice=3 DRUG, ETC)? Monthly=4 Weekly=5 Daily/Almost daily=6 4. During the past three months, how often has your use of (FIRST DRUG, SECOND DRUG, ETC) led to health, once/Twice=4 social, legal or financial problems? Monthly=5 Weekly=6 Daily/Almost daily=7 5. During the past three months, how often have you failed to do what was normally expected of you because of you once/Twice=5 because of your use of (FIRST DRUG, SECOND DRUG, Monthly=6 ETC)? Weekly=7 Daily/Almost daily=8 6. Has a friend or relative or anyone else expressed concern No, never=0
DRUG, ETC)? Monthly=4 Weekly=5 Daily/Almost daily=6 4. During the past three months, how often has your use of (FIRST DRUG, SECOND DRUG, ETC) led to health, Once/Twice=4 social, legal or financial problems? Monthly=5 Weekly=6 Daily/Almost daily=7 5. During the past three months, how often have you failed to do what was normally expected of you because of you Once/Twice=5 because of your use of (FIRST DRUG, SECOND DRUG, Monthly=6 ETC)? Weekly=7 Daily/Almost daily=8 6. Has a friend or relative or anyone else expressed concern No, never=0
Weekly=5 Daily/Almost daily=6 4. During the past three months, how often has your use of (FIRST DRUG, SECOND DRUG, ETC) led to health, Once/Twice=4 social, legal or financial problems? Monthly=5 Weekly=6 Daily/Almost daily=7 5. During the past three months, how often have you failed to do what was normally expected of you because of you Once/Twice=5 because of your use of (FIRST DRUG, SECOND DRUG, Monthly=6 ETC)? Weekly=7 Daily/Almost daily=8 6. Has a friend or relative or anyone else expressed concern No, never=0
4. During the past three months, how often has your use of (FIRST DRUG, SECOND DRUG, ETC) led to health, Once/Twice=4 social, legal or financial problems? Monthly=5 Weekly=6 Daily/Almost daily=7 5. During the past three months, how often have you failed to do what was normally expected of you because of you Once/Twice=5 because of your use of (FIRST DRUG, SECOND DRUG, Monthly=6 ETC)? Weekly=7 Daily/Almost daily=8 6. Has a friend or relative or anyone else expressed concern No, never=0
 4. During the past three months, how often has your use of (FIRST DRUG, SECOND DRUG, ETC) led to health, Once/Twice=4 social, legal or financial problems? Monthly=5 Weekly=6 Daily/Almost daily=7 5. During the past three months, how often have you failed to do what was normally expected of you because of you Once/Twice=5 because of your use of (FIRST DRUG, SECOND DRUG, Monthly=6 ETC)? Weekly=7 Daily/Almost daily=8 6. Has a friend or relative or anyone else expressed concern No, never=0
(FIRST DRUG, SECOND DRUG, ETC) led to health, Once/Twice=4 social, legal or financial problems? Monthly=5 Weekly=6 Daily/Almost daily=7 5. During the past three months, how often have you failed to do what was normally expected of you because of you Once/Twice=5 because of your use of (FIRST DRUG, SECOND DRUG, Monthly=6 ETC)? Weekly=7 Daily/Almost daily=8 6. Has a friend or relative or anyone else expressed concern No, never=0
social, legal or financial problems? Monthly=5 Weekly=6 Daily/Almost daily=7 5. During the past three months, how often have you failed to do what was normally expected of you because of you Once/Twice=5 because of your use of (FIRST DRUG, SECOND DRUG, Monthly=6 ETC)? Weekly=7 Daily/Almost daily=8 6. Has a friend or relative or anyone else expressed concern No, never=0
Weekly=6 Daily/Almost daily=7 5. During the past three months, how often have you failed to do what was normally expected of you because of you Once/Twice=5 because of your use of (FIRST DRUG, SECOND DRUG, Monthly=6 ETC)? Weekly=7 Daily/Almost daily=8 6. Has a friend or relative or anyone else expressed concern No, never=0
5. During the past three months, how often have you failed to do what was normally expected of you because of you once/Twice=5 because of your use of (FIRST DRUG, SECOND DRUG, Monthly=6 ETC)? Weekly=7 Daily/Almost daily=8 6. Has a friend or relative or anyone else expressed concern No, never=0
 5. During the past three months, how often have you failed to do what was normally expected of you because of you because of you because of your use of (FIRST DRUG, SECOND DRUG, Monthly=6 ETC)? 6. Has a friend or relative or anyone else expressed concern No, never=0
because of your use of (FIRST DRUG, SECOND DRUG, Monthly=6 ETC)? Weekly=7 Daily/Almost daily=8 6. Has a friend or relative or anyone else expressed concern No, never=0
ETC)? Weekly=7 Daily/Almost daily=8 6. Has a friend or relative or anyone else expressed concern No, never=0
Daily/Almost daily=8 6. Has a friend or relative or anyone else expressed concern No, never=0
6. Has a friend or relative or anyone else expressed concern No, never=0
•
about your use of (FIRST DRUG, SECOND DRUG, Yes, in the past 3
· · · · · · · · · · · · · · · · · · ·
ETC.)? months=6
Yes, but not in the past 3
months=3
7. Have you ever tried and failed to control, cut down or stop No, never=0
using (FIRST DRUG, SECOND DRUG, ETC.)? Yes, in the past 3
months=6
Yes, but not in the past 3 months=3
8. Have you ever used any drug by injection? (NON- No, never=0
MEDICAL USE ONLY) MEDICAL USE ONLY) Yes, in the past 3
months=2

If yes, ask pattern of injecting	Yes, but not in the past 3 months=1 Once weekly/less or <3 days in a row
	>1 per week or ≥3 days in a row

Scoring a specific substance involvement score

For example: Cannabis= Q2c+Q3c+Q4c+Q5c+Q6c+Q7c

Only for tobacco= Q2a+Q3a+Q4a+Q6a+Q7a

Interpretation of score and type of intervention

- Low: You are at low risk of health and other problems from your current pattern of use.
- Moderate: You are at risk of health and other problems from your current pattern of substance use.
- High: You are at high risk of experiencing severe problems (health, social, financial, legal, High: relationship) as a result of your current pattern of use and are likely to be dependent

Substances	Risk and type of intervention							
	✓ General health advice	✓ Receive brief intervention✓ Take home information	 ✓ Receive brief intervention ✓ Take home information ✓ Referral to specialist assessment and treatment 					
	(Low risk)	(Moderate risk)	(High risk)					
Tobacco	0-3	4-26	27+					
Alcohol	0-10	11-26	27.					
•		11 20	27+					
Cannabis	0-3	4-26	27+					
Cannabis Amphetamine								
	0-3	4-26	27+					
Amphetamine	0-3 0-3	4-26 4-26	27+ 27+					
Amphetamine Inhalants	0-3 0-3 0-3	4-26 4-26 4-26	27+ 27+ 27+					
Amphetamine Inhalants Sedatives	0-3 0-3 0-3 0-3	4-26 4-26 4-26 4-26	27+ 27+ 27+ 27+					

